3.4 Subject Selection

The subjects will be selected from patients presenting to the services of Obstetrics and Gynecology at Robert Wood Johnson University Hospital in New Brunswick, NJ.

Reducing Nausea and Vomiting During Cesarean Section with Regional Anesthesia: Is the Application of Scopolamine Patch with or without Intra-operative Acupressure Point P6 Stimulation more effective than Intra-operative Acupressure Point P6 Stimulation alone?

By [name]

3.4.1 Inclusion Criteria

- (1) Female subjects ages 18 to 45
- (2) Subjects with ASA Class I or II
- (3) Subjects with elective primary or repeat cesarean delivery
- (4) Subjects who receive spinal and/or epidural anesthesia
- (5) English and non-English speaking subjects will be included in the study

3.4.2 Exclusion Criteria

- (1) Female subjects <18 years of age
- (2) Subjects requiring emergent cesarean delivery
- (3) Gestational age < 37 weeks
- (4) History of placenta accreta
- (5) Multiple gestation pregnancy
- (6) ASA status III or higher
- (7) Current history of pregnancy induced hypertension, pre-eclampsia, or eclampsia
- (8) History of any chronic medication use (other than prenatal vitamins), including inhaler medications
- (9) Current urinary tract infection, pneumonia, or otitis media
- (10) Coagulopathies or skin infections overlying the spine
- (11) History of open angle glaucoma, seizures or psychosis

4. Study Variables

4.1 Independent Variables or Interventions

Subjects in Group I will receive prophylactic scopolamine patch. Subjects in Group II will receive acupressure point P6 stimulation. Subjects in Group III will receive both scopolamine patch and acupressure point P6 stimulation. All three interventions are the standard of care at RWJUH.

4.1.1 Drug or Device Interventions

Subjects randomized to Group I will receive scopolamine patch on the skin behind the right ear 1 hour prior to administration of the standardized regional anesthesia. Subjects randomized to Group II will receive acupressure point P6 stimulation to the right forearm. This consists of a device that releases continuous electric shocks at a level that is comfortable for the patient over the P6 acupressure point. Subjects randomized to Group III will receive both scopolamine patch and acupressure point P6 stimulation. The time at which the patch will be placed on the patient will be recorded. All RWJUH policy will be followed for device and drugs storage, access, and control.

4.2 Dependent Variables or Outcome Measures

The study instrument that we will use is an assessment flowsheet to document:

1. ASA class
2. Age
3. Height

Reducing Nausea and Vomiting During Cesarean Section with Regional Anesthesia: Is the Application of Scopolamine Patch with or without Intra-operative Acupressure Point P6 Stimulation more effective than Intra-operative Acupressure Point P6 Stimulation alone?

By [name]

4. Gestational Age
5. Apfel Score (1-4)
6. Hypertension (systolic blood pressure greater than 140) (yes or no)
7. Highest Blood Pressure
8. Hypotension (Did blood pressure drop below 90 systolic at any point) (yes or no)
9. Hypoxia (Did intra-operative pulse oximetry drop <85 %?) (yes or no)
10. Lowest Pulse Oximetry (%)
11. Has Patient Vomited During Procedure (yes or no)
12. Did Patient Vomit After Administration of regional anesthesia (yes or no)
13. Did Patient Vomit After Eversion of Uterus (yes or no)
14. Did Patient Vomit After Replacement of Uterus (yes or no)
15. Did Patient Vomit Upon Arrival to Post-Operative Recovery Room (yes or no)
16. Has Patient Had Nausea During Procedure (yes or no)
17. Ranked Nausea After Administration of regional anesthesia (0-10, 0 = no nausea, 10 = worst nausea ever experienced)
18. Ranked Nausea After Eversion of Uterus (0-10, 0 = no nausea, 10 = worst nausea ever experienced)
19. Ranked Nausea After Replacement of Uterus (0-10, 0 = no nausea, 10 = worst nausea ever experienced)
20. Ranked Nausea Upon Arrival to Post-Operative Recovery Room (0-10, 0 = no nausea, 10 = worst nausea ever experienced)
21. Did Patient Have >700cc Blood Loss (yes or no), amount of blood loss _____
22. Efficacy of Sensory Block for Cesarean Section (1 = No Complaints, 2 = + Complaints, 3 = + Sedation N₂O or IV, 4 = G/A)
23. Nausea and Vomiting Treatment Satisfaction (0 = Not Satisfied, 10 = Extremely Satisfied)
24. Overall Satisfaction (0 = Not Satisfied, 10 = Extremely Satisfied)

4.3 Chart Review Selection

No subject charts will be reviewed since this is not a retrospective study.

4.4 Risks of Harm

Common adverse effects of scopolamine patch include: dry mouth, drowsiness, dizziness, blurred vision, and mydriasis. Rare but serious side effects include disorientation, memory disturbances, dizziness, restlessness, giddiness, hallucinations, delirium, and confusion[10].

The application of the acupressure point P6 stimulator may rarely cause potential discomfort during the intervention.

There is a potential for loss of anonymity; however, every safety measure will be in place to prevent any breeches in confidentiality.

Reducing Nausea and Vomiting During Cesarean Section with Regional Anesthesia: Is the Application of Scopolamine Patch with or without Intra-operative Acupressure Point P6 Stimulation more effective than Intra-operative Acupressure Point P6 Stimulation alone?

By **[name]**

There are no known psychological/emotional, social, legal, and economic risks of harm from the acupressure point P6 stimulation.

4.5 Potential for Benefit

Potential benefits from the use of acupressure point P6 stimulation include:

1. Reduction of intra-cesarean section nausea and vomiting
2. Potential reduction in cost from using medical therapy (scopolamine patch)
3. Potential reduction of negative side effects associated with medical therapy (scopolamine patch)
4. Potential change of standard of care from more costly medical therapy (scopolamine patch) that can cause potential adverse effects to the more cost effective acupressure point P6 stimulation which has very little side effects associated with its use.

5. Subject Recruitment and Enrollment Considerations

5.1 Subject Recruitment

Subjects presenting to the Obstetrics and Gynecology Services for elective cesarean section or repeat cesarean section who will be undergoing spinal, epidural or combined spinal epidural anesthesia will be approached for consideration of the study. The following times will be documented: when the patient is approached, when the consent form is signed, when the patch is applied on the patient, when the acupressure point P6 stimulation device is applied, and when the surgery begins.

5.2 Consent Procedures

The informed consent process will begin after a subject presents to the Obstetrics and Gynecology Services for elective cesarean section. It will take place while the patient is in the holding room. The patient is in the holding room for a significant amount of time prior to the surgery. This is the time when the nurse approaches the patient to get all the patient's necessary medical records into the computer. During this time, the surgeon and anesthesiologist approach the patient to get consent for the operation and for the anesthesia. With the explanation of the anesthesia, the patient will also be explained about the opportunity to participate in the study. If the patient chooses to participate in the study, the patient will receive the same standard of care that she would have received if she were not part of the study. The only difference is that if the patient is not part of the study, each anesthesiologist chooses by him or herself one of the three options that the patient will receive for anti-nausea medication. If the patient chooses to be part of the study, no matter which anesthesiologist will be at the surgery, the choice of which anti-nausea medication that the patient receives will be random. Each individual will be explained this and given the informed consent document to read and consider prior to agreeing to participate. The study investigator will answer all the subjects' questions and ensure the subject has adequate time to consider participation prior to signing the informed consent document. The patient will be told that she can think about it and does not need to sign the consent form at this time if she does not choose to. No study assessments, measurements, or interventions will occur prior to the subject signing the informed consent document.

Reducing Nausea and Vomiting During Cesarean Section with Regional Anesthesia: Is the Application of Scopolamine Patch with or without Intra-operative Acupressure Point P6 Stimulation more effective than Intra-operative Acupressure Point P6 Stimulation alone?

By **[name]**

We are going to obtain consent from subjects to participate in this study prior to the initiation of study interventions.

The following members of the research team will be obtaining consent from patients: [name] and [name].

[name] will educate all members of the research team how to obtain appropriate consent. He will demonstrate how to obtain the consent until he feels comfortable that the research team members can obtain the consent by themselves.

The details of the study will be communicated to the patients' obstetricians via email prior to beginning the study. The obstetricians will direct their questions regarding the study to [name]. [name] will speak with the obstetricians in the holding room and explain to them the study.

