1.1 Objectives

The objective is to randomize subjects who undergo cesarean section with regional anesthesia into one of three groups to compare the efficacy of the therapies. Subjects will receive either (1) scopolamine patch or (2) acupressure point P6 stimulation or (3) scopolamine patch and acupressure point P6 stimulation to reduce intra-cesarean section nausea and vomiting.

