The acupressure point P6 stimulation device is FDA approved for monitoring the magnitude of neuromuscular blocks in general anesthesia. This device stimulates the P6 acupressure point, which as demonstrated in previously published studies, is a safe acupressure point to be stimulated in pregnant women[14, 15]. However, to our knowledge, there are no published studies that have compared the effectiveness of this device versus the scopolamine patch versus the combination of the scopolamine patch and this device in preventing nausea and vomiting in women undergoing cesarean section under regional anesthesia. In this study, we would like to compare these three methods. The device will be used off-label in our study.

As per the RWJUH Obstetric Anesthesia Guidelines (Page 11, Section III B), metoclopramide, ondansetron, scopolamine patch, and acupressure point P6 stimulation may be applied prophylactically or therapeutically for the commonly complaints of nausea and vomiting.

Today, there are five types of procedures that are considered standard of care for obstetric patients undergoing cesarean section with regional anesthesia at the RWJUH. Each doctor gets to choose what he or she wants to do because for now, it is unclear which method is the best. (1) It is acceptable to not give any prophylactic nausea/vomiting therapy at the start of the anesthesia, (2) administer prophylactic metoclopramide and odansetron before beginning the anesthesia, (3) administer scopolamine patch prophylactically before beginning the procedure, (4) stimulate the P6 acupressure point before the start of the anesthesia and continue stimulating it throughout the procedure, or (5) administer scopolamine patch along with acupuncture point P6.

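### Protocol sections 3 and 5.2 disagree on how many anti-nausea options a woman has outside the study, and section 5.2 sets what she is told at consent

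*Protocol*

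**What the plan says.** Protocol section 3 (Research Design and Methods) describes current practice at the hospital: "Today, there are five types of procedures that are considered standard of care for obstetric patients undergoing cesarean section". It adds: "Each doctor gets to choose what he or she wants to do because for now, it is unclear which method is the best". The list that follows has five entries. The first is giving no prophylaxis at the start of anesthesia. The second is to "administer prophylactic metoclopramide and odansetron before beginning the anesthesia". The remaining three are the scopolamine patch, P6 stimulation, and the two together.

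Protocol section 1.1 gives the randomized arms: "Subjects will receive either (1) scopolamine patch or (2) acupressure point P6 stimulation or (3) scopolamine patch and acupressure point P6 stimulation".

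Protocol section 5.2 (Consent Procedures) describes the alternative to taking part. Outside the study, "each anesthesiologist chooses by him or herself one of the three options that the patient will receive for anti-nausea medication"; inside it, the choice is random. The section says that a participant gets the standard of care she would have had anyway, and that the way the choice is made is the one thing that changes. It then directs that this be explained to each woman, who also receives the consent document to read.

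Two other places bear on the point. Section 4.1 states that all three study interventions are standard of care at the hospital. Section 3 also provides that a woman in any arm who reports nausea or vomiting during the operation receives ondansetron, with or without metoclopramide, as rescue.

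**The concern.** A woman deciding whether to join needs to know what she would otherwise receive. Section 5.2 sets out that account, and on the number of options it conflicts with section 3 of the same protocol. If section 3 describes practice correctly, a woman whose doctor would have given no prophylaxis, or prophylactic metoclopramide with ondansetron, would have her initial management changed by joining. The prescribed explanation would tell her that only the manner of choosing differs.

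Two of the three arms (80 + 80 = 160 of the 240 planned subjects) receive scopolamine. Sections 2 and 4.4 list its common effects and its rare but serious ones, so the absence of a no-prophylaxis option is something a woman could reasonably weigh.

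**Working it through.** No formula applies. The check is a count and a comparison of lists.

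**Step 1: the count in section 5.2.** The stated figure is three options outside the study. Section 5.2 does not name them. The only list of three in the protocol is the list of study arms (sections 1.1, 3 and 4.1).

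**Step 2: the count in section 3.** The stated figure is five, and five are listed.

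| Option listed in section 3 | Study arm? |
|---|---|
| No prophylaxis at the start of anesthesia | No |
| Prophylactic metoclopramide and ondansetron | No |
| Scopolamine patch | Yes, Group I |
| P6 stimulation | Yes, Group II |
| Patch and P6 stimulation | Yes, Group III |

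**Step 3: the difference.** 5 listed − 3 that match an arm = 2 that randomization cannot assign. The figure of three in section 5.2 is therefore not reproduced from section 3.

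**Step 4: does any other text resolve it?**
- Section 4.1 says the three study interventions are standard of care. That is equally true if they are three of five, so it does not decide the matter.
- The hospital guideline cited in section 3 is reported as allowing metoclopramide, ondansetron, the patch and P6 stimulation, either prophylactically or therapeutically. That fits the longer list but does not say how many strategies anesthesiologists use in practice.
- The rescue provision in section 3 keeps ondansetron, with or without metoclopramide, available in every arm, but only after symptoms. It does not replace the prophylactic option, and it has no bearing on the no-prophylaxis option.

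**Step 5: does the statement reach participants?** Section 5.2 directs that each individual have it explained to her. It is part of the consent procedure as written.

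**Step 6: size.** On section 3's account, two of five listed initial strategies are closed to a participant and go unmentioned. The share of women whose doctor would have chosen one of those two is not given. It could lie anywhere between none and all, and the documents do not narrow the range.

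**The case against.** The strongest reply is that section 5.2 may simply be shorthand. Read loosely, its three options are the three study arms, each of which section 4.1 calls standard of care, so a participant does receive standard care of one kind or another. Each woman also gets a written consent document and may put questions to the investigator, and that document may describe usual care in full. Part of this stands: every arm is a listed standard-of-care option, and the consent form was not among the material reviewed. It does not remove the conflict. Section 5.2 is speaking of what the anesthesiologist chooses for women outside the study, and section 3 gives a different number for the same choice.

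Four stronger readings are tempting, and the documents do not support them.

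- *That women were in fact misinformed.* This would require the consent form or a record of what was said. What can be shown is that section 5.2, followed as written, conflicts with section 3.
- *That section 5.2 is the section in error.* Section 3 is the more explicit text, but which list reflects practice is a fact about the hospital that the protocol states in two ways. It is for the investigators to settle.
- *That 40% of care, or 400 women, is affected.* Two of five is a count of list entries, not a share of patients. The 400 in section 6 is a ceiling on consent signatures; 240 subjects are planned.
- *That the trial claims to find the best of all usual-care options.* Section 3's remark that the best method is unclear explains why doctors choose freely. Sections 1, 1.1, 1.2, 2 and 3 already confine the question to the three arms, and section 3.3 powers only the combination against each single method. Leaving out the other two options as comparators is a design choice.

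**Conclusion.** The inconsistency is real and unresolved: five usual-care options in section 3, three in section 5.2. It is more than clerical, because section 5.2 prescribes what each woman is told about the alternative to joining.

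The consequence is conditional. If section 3 is correct, the prescribed explanation omits that participation rules out two initial options, no prophylaxis and prophylactic metoclopramide with ondansetron, and its assurances that care is unchanged and that only the manner of choosing differs need qualifying. If section 5.2 is correct, the explanation stands on this point and section 3 misdescribes practice.

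The conclusion rests on the protocol text alone and assumes that the explanation is given as section 5.2 directs. It does not touch sample size, power, the significance level, the endpoints or the analysis, and it does not undermine the randomized comparison. The correction should be made because it concerns consent and costs little.

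**What to change.** Reconcile sections 3 and 5.2 of the protocol.

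- If five options is the accurate account, amend section 5.2 and the explanation given at consent. List every usual-care option, say that participation limits the initial choice to the three study arms, and remove or qualify the statements that care is the same and that random choice is the sole difference. It would be accurate to add that ondansetron, with or without metoclopramide, is provided in the trial as rescue.
- If three options is the accurate account, amend the list in section 3.
- In either case, check the consent form for the same statement and bring it into line. The SAP describes its methods in the past tense, so enrolment may already be over. If it is, make the correction in the protocol record and in the description of usual care in any report, and have the sponsor check what participants were told.

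No change is needed to section 1.1 or section 9.3. The cost is a wording amendment to the protocol and, where needed, to the consent material. If women are still being recruited, a few may decline once the other options are named.

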5.3 Subject Costs and Compensation

The subject will not incur additional costs outside of standard of care costs for medication that may be performed for routine standard of care. There will be no compensation for participation in this study.

6. Data Handling

All data will be stored in a locked file in the office of the principal investigator with limited access. The link to the protected health information will be stored separately from the study files and will be destroyed after all the data has been collected and analyzed. Up to 400 subjects may sign the informed consent for participating in this trial. This number is to ensure that 80 subjects complete each study group below. Therefore, we will be replacing subjects that do not complete the study as designed.

7. Statistical Analysis

There will be 3 treatment groups each having 80 subjects enrolled for the study. The intergroup analysis for numerical variables will be performed by ANOVA. All categorical variables will be analyzed with Chi-square/Fisher test. Descriptive statistics will provide the quantitative summaries for numerical data in each group.

The difference in end surgical nausea and vomiting will be analyzed using the Mann-Whitney rank sum test. Power analysis determined that 80 patients will be necessary in each group to detect the difference in treatment in nausea and vomiting, assuming a two sided alpha of 0.05 and power of 90%.

8. Data and Safety Monitoring

There is no data and safety monitoring committee for this study. Patients will be followed for adverse effects during their participation in this study. We will use Form FDA 3500A mandatory and Form FDA 3500 voluntary reporting forms found on the FDA website, www.fda.gov.

Reducing Nausea and Vomiting During Cesarean Section with Regional Anesthesia: Is the Application of Scopolamine Patch with or without Intra-operative Acupressure Point P6 Stimulation more effective than Intra-operative Acupressure Point P6 Stimulation alone?

By [name]

9. Reporting Results

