As evidenced above, the drugs currently used to prevent intra- and post-cesarean section nausea and vomiting are not without side effects. Other less expensive and safer alternatives have also been used with varying degrees of effectiveness in the treatment of perioperative nausea and vomiting. One non-pharmacological agent, P6 acupressure point stimulation, has been shown to be effective in reduction of post-operative nausea and vomiting. Based on the meta-analysis of 40 trials, involving 4858 patients, it was concluded that there is no differences in risks of postoperative nausea or vomiting after P6 acupressure point

Reducing Nausea and Vomiting During Cesarean Section with Regional Anesthesia: Is the Application of Scopolamine Patch with or without Intra-operative Acupressure Point P6 Stimulation more effective than Intra-operative Acupressure Point P6 Stimulation alone?

By **[name]**

stimulation compared to after administration of antiemetic drugs[12]. Additionally, the application of the acupressure point P6 stimulator has no known risks except for potential mild discomfort of the arm. However, only a few studies have been performed to determine if acupressure point P6 stimulation is effective in reducing intracesarean section nausea and vomiting under regional anesthesia, and the results are inconclusive[13].

In our study, we would like to compare the effectiveness of antiemetic agents or technique which cause less severe adverse reactions to the mother and her fetus. Out of the available pharmacological agents for reduction of intra-cesarean section nausea and vomiting, transdermal scopolamine patch is one of the safest medications. We would like to compare the effectiveness of the transdermal scopolamine patch with acupressure point P6 stimulation versus just transdermal scopolamine patch versus just acupressure point P6 stimulation.

3. Research Design and Methods

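### Adverse-effect follow-up is promised and fewer side effects are claimed for P6, but no form item or SAP table covers the expected patch or P6 effects, so tolerability cannot be compared systematically between arms

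*Protocol*

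**What the plan says.** **Rationale.** Protocol Section 2 describes P6 among cheaper and safer alternatives to drugs, and says the aim is to "compare the effectiveness of antiemetic agents or technique which cause less severe adverse reactions to the mother and her fetus". Section 4.5 lists among the potential benefits of P6 "Potential reduction of negative side effects associated with medical therapy (scopolamine patch", and adds a possible move of standard of care away from the patch, partly because P6 has few side effects.

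**Expected effects.** Section 4.4 is specific: "Common adverse effects of scopolamine patch include: dry mouth, drowsiness, dizziness, blurred vision, and mydriasis". It also names rarer central nervous system effects such as delirium and confusion. For the device it says: "The application of the acupressure point P6 stimulator may rarely cause potential discomfort during the intervention".

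**Follow-up.** Section 8 says "Patients will be followed for adverse effects during their participation in this study" and "We will use Form FDA 3500A mandatory and Form FDA 3500 voluntary reporting forms found on the FDA website". It gives no checklist, time of questioning, grading or summary by arm, and says there is no monitoring committee.

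**Data collection.** Section 4.2 introduces its list with "The study instrument that we will use is an assessment flowsheet to document". Appendix I is the matching form, and Appendix II is a nausea score.

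**Analysis.** The SAP Methods cover satisfaction, nausea ratings, and the occurrence of nausea and vomiting. Adverse effects do not appear.

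**The concern.** The protocol makes a side-effect argument and a follow-up commitment, but names no place where the relevant data would be written down. The FDA forms report individual events. Nothing in the documents ties them to asking every woman the same question, so they give no reliable numerator by arm. The trial is also open-label (Section 3), so effects that nobody asks about may be noticed and recorded unevenly between women with and without a patch.

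What is at stake is interpretation. If the combination or the patch reduces nausea and vomiting, the gain cannot be set against any added side effects. If P6 alone performs as well, its supposed tolerability advantage can be neither shown nor refuted. Symptoms not asked about at the time cannot be recovered afterwards.

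**Working it through.** **Step 1: the form against the named effects.** The 24 items in Section 4.2 group as follows:

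| Items | Content |
|---|---|
| 1–5 | Baseline: ASA class, age, height, gestational age, Apfel score |
| 6–10 | Blood pressure and oximetry |
| 11–15 | Vomiting |
| 16–20 | Nausea |
| 21 | Blood loss |
| 22 | Efficacy of the sensory block |
| 23–24 | Satisfaction |

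The count is 5 + 5 + 5 + 5 + 1 + 1 + 2 = 24. Items 6–10 and 21 are intraoperative safety measures. None of the 24 records a patch effect or the device discomfort named in Section 4.4. Item 22 notes whether sedation was given, which is not drowsiness as a side effect. Appendix I adds weight, lowest blood pressure and several clock times, but no adverse-effect item and no free-text event field.

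**Step 2: the planned arm size.** The documents plan no adverse-effect comparison, so the only figure to reproduce is 80 per arm (Section 3.3: 90% v 70% success, two-sided 5%, power 90%). With unpooled variance:

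n = (1.960 + 1.282)² × (0.9×0.1 + 0.7×0.3) / 0.2² = 78.8, so 79 per arm.

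The pooled-variance formula gives 82. The stated 80 is consistent with both, and 80 per arm is used below.

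**Step 3: which contrasts isolate each component.**
- Group III v II: both have the device, and only III has the patch. This estimates the patch effect.
- Group III v I: both have the patch, and only III has the device. This estimates device discomfort.
- Groups I + III v II (160 v 80): Group I lacks the device that Group II has, so patch and device are mixed.

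**Step 4: what 80 v 80 would deliver.** The documents give no adverse-effect rates, so the rates below are assumptions across a range. Half-width = 1.96 × √[p₁(1−p₁)/80 + p₂(1−p₂)/80]. For 20% v 5%: 1.96 × √(0.16/80 + 0.0475/80) = 1.96 × 0.0509 = 10.0 points. Power is the exact binomial power of the uncorrected chi-square test at two-sided 5%.

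| Assumed rates | Difference | 95% CI half-width | Power |
|---|---|---|---|
| 20% v 5% | 15 points | 10.0 points | 85% |
| 25% v 10% | 15 points | 11.5 points | 72% |
| 15% v 5% | 10 points | 9.2 points | 57% |
| 10% v 5% | 5 points | 8.1 points | 21% |

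For rare effects, zero events in 80 women gives a one-sided 95% upper limit of 1 − 0.05^(1/80) = 3.7%.

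**The case against.** The strongest reply is that tolerability is not a question this trial set itself. Sections 1, 1.1 and 1.2 concern nausea and vomiting only. The Section 2 sentence says that effectiveness is compared; lower toxicity explains the choice of treatments, and the next sentence calls the patch one of the safest drugs. Section 4.5 lists hoped-for benefits, not endpoints. The SAP's opening comment frames it as methods for effectiveness. All of this stands, and it limits the point: no stated objective goes unmet.

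A reader might infer that the trial has no safety data at all. The documents do not support that, because blood pressure, oximetry and blood loss are recorded. A reader might also infer that adverse effects will be captured only if women volunteer them. Section 8 does not say so; it leaves the method open.

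The remedy has limits too. Answers would still be open-label self-reports, and rescue antiemetics or sedation could influence some symptoms. One question on arrival in recovery covers only what is apparent by then. What survives is that the protocol makes the side-effect claim and the follow-up promise, and neither has a data item behind it. A 0–10 satisfaction score cannot stand in for named symptoms.

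**Conclusion.** The point holds as a gap in data collection and reporting. None of the 24 items records an expected patch or P6 effect, there is no general adverse-event field, and the SAP has no summary. Tolerability therefore cannot be compared systematically between arms from the planned data.

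It should not be read as a threat to the nausea and vomiting comparison, which is unaffected. Nor should it be read as showing that the trial could settle tolerability if the items were added. Pooling both patch arms against P6 alone gives a more flattering 92.7% power for 20% v 5% and 82.0% for 25% v 10%, but those figures assume 15-point differences and use a contrast that mixes in the device. With the clean 80 v 80 contrast, power falls to 85% and 72%, and to 57% or 21% for differences of 10 or 5 points. Rare serious effects would remain unassessable. All these rates are assumptions.

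The text between protocol Sections 3.1 and 3.3 and the opening pages of the SAP were not available to check. The flowsheet and form are listed in full.

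**What to change.** **Form.** Add to Appendix I, and to the list in Section 4.2, yes/no items for the effects already named in Section 4.4 (the rarer central effects can share one item) and an open field for anything else. Ask them identically in all three arms at the existing assessment on arrival in recovery. State in Section 8 that this is how adverse effects are elicited.

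**SAP.** Add one table of counts and percentages by arm, with risk differences and 95% confidence intervals: Group III v II for patch effects and Group III v I for device discomfort. Label it descriptive, since several symptoms are examined and the trial is not sized for them.

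**Cost.** About a minute of questioning per woman and one table.

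**If data collection is finished.** The SAP is written in the past tense, so this may already be the case, and new items could then no longer help. In that case, tabulate by arm whatever adverse effects were recorded, state that they were unsolicited, and make no comparative tolerability claim.
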